15.6 Statistical Analyses

15.6.1 General Approach

Descriptive statistics will be used to summarize all data including mean, median, standard deviation, inter-quartile range etc. for continuous data and count and percentages for categorical data. Data will be analyzed as observed and no data imputation will be performed. Statistical significance is set at 5% level.

15.6.2 Analysis of the Primary Endpoint(s)

The primary endpoint ORR assessed by investigator review will be analyzed using the efficacy analysis set. ORR will be calculated as the proportion of patients who achieves the BOR of either CR or PR per RECIST v1.1 and the 95% Clopper-Pearson exact CI will be derived.

The right-side one-sample binomial exact test will be conducted to test the hypothesis testing as follows:

$$H_0: \text{ORR} \leq 15\% \text{ vs. } H_a: \text{ORR} \geq 35\%.$$

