2.6 Study Design

2.6.1 Overall Design

This is a single-arm, multicenter, phase 2 study of lenvatinib in combination with pembrolizumab (lenvatinib 20 mg/day + pembrolizumab 200mg q3weeks) in subjects with unresectable advanced or metastatic nccRCC who have not received any chemotherapy for advanced disease.

A Simon's Two-Stage Design will be implemented in approximately 34 enrolled subjects. Nine subjects will be enrolled in Stage 1. If there are at least 2 responders

as assessed by ORR, the study will proceed to Stage 2 in which 25 more subjects may be enrolled. Otherwise, the study will stop early for futility. In the final analysis of 34 subjects, at least 9 responders are required to show a statistically significant improvement of ORR over historical control in the same patient population (one-sided type I error of 5% and targeting for 80% power).

This study consists of 3 phases:

1. Pre-treatment phase (Screening Periods)
2. Treatment phase (starting Cycle 1 Day 1)
3. Post-treatment phase (End of Treatment Visit and survival follow-up)

The pre-treatment phase is planned to last no longer than 21 days and will include a screening period to establish protocol eligibility.

The treatment phase will begin at the time of study drug administration on Day 1 of Cycle 1 and continue in 21-day (3-week) cycles until completion of the off-treatment assessments (within 30 days after the last study drug administration). Lenvatinib 20 mg/day will be administered orally on a daily basis and pembrolizumab 200 mg will be infused once every 3 weeks. Subjects will undergo safety and efficacy assessments. Toxicity will be managed by treatment interruption, dose reduction and/or treatment discontinuation. Subjects who discontinue one of the study drugs due to its toxicities may continue to receive the other study drug as long as they demonstrate clinical benefit. Subjects will discontinue both study drugs at the time of confirmed disease progression, development of unacceptable toxicity, withdrawal of consent, or study termination. Subjects may be treated with pembrolizumab for a maximum of 35 cycles or approximately 2 years, but treatment with lenvatinib can continue beyond 2 years if the subject does not meet other treatment discontinuation criteria.

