15.4 Sample Size Determination

The Simon's Two-Stage optimal design was adopted to design the study with a one-sided type I error rate of 5% and targeting for 80% power. Approximately 34 efficacy evaluable subjects will be enrolled. During the 1st stage, 9 subjects will be enrolled and if there are ≥ 2 responders as assessed by ORR, the study will proceed to Stage 2 in which 25 new subjects will be enrolled; otherwise, the study will stop early for futility. In the final analysis of 34 efficacy evaluable subjects, ≥ 9 responders are required to claim preliminary efficacy of the treatment combination over historical control in the same patient population.

The actual alpha level was 0.047 and the actual power was 0.811. The early termination probability is estimated at 0.5995 if null is true and the average sample size is around 19.

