15.6.5 Planned Interim Analysis

An interim analysis for futility will be performed based on the Simon's 2-stage optimal design when 9 efficacy evaluable patients are evaluable for ORR. The study will stop early if 2 or fewer responders are observed. If 3 or more responders are confirmed before the planned interim analysis and the safety profiles of both drugs are acceptable, the study will continue to Stage 2 and a normal interim analysis may be waived. There will be no enrollment gap for the interim analysis.

At the final analysis with 34 efficacy evaluable patients, the study will claim preliminary efficacy to warrant further study if 9 or more responders are observed.

	Threshold
Interim Analysis	Continue to enroll if ≥ 2 responders among the first 9 efficacy evaluable patients
Final Analysis	Reject H_0 if ≥ 9 responders among n=34 patients

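### The exact binomial test named for ORR in 15.6.2 ignores the stage-1 stop and gives p = 0.0587 at 9/34, a result the plan elsewhere counts as success

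*Combined protocol and SAP*

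**What the plan says.** The design is Simon's optimal two-stage design for 15% versus 35%, at one-sided 5% with 80% power targeted (15.3, 15.4). Stage 1 has 9 patients. The study continues if at least 2 respond (2.6.1, 15.4 and the 15.6.5 table) and then adds 25, for 34 in total.

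The success rule is stated several times:

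- 2.6.1: "at least 9 responders are required to show a statistically significant improvement of ORR over historical control".
- 15.4: at least 9 "responders are required to claim preliminary efficacy of the treatment combination over historical control in the same patient population", with operating characteristics given as "The actual alpha level was 0.047 and the actual power was 0.811".
- 15.6.5, text: "the study will claim preliminary efficacy to warrant further study if 9 or more responders are observed".
- 15.6.5, table: "Reject H_0 if ≥ 9 responders among n=34 patients".

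Section 15.6.2, which defines the primary analysis, names a procedure instead: "The right-side one-sample binomial exact test will be conducted to test the hypothesis testing as follows", for a null of at most 15%. It also asks for a 95% Clopper-Pearson interval. It does not cite 15.4 or 15.6.5 and gives no cutoff. Section 15.6.1 adds "Statistical significance is set at 5% level". Nothing says which rule prevails if the test and the boundary disagree. The total is also not fixed: 15.4 says "Approximately 34 efficacy evaluable subjects will be enrolled".

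**The concern.** A one-sample exact binomial test treats all 34 patients as a single fixed sample. Its upper tail therefore includes paths with 0 or 1 responders in the first 9 that later reach 9 or more. The design stops those paths, so they cannot lead to rejection. The test's p-value at the boundary is therefore larger than the design's alpha, and the question is whether it crosses 5%.

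It does. A programmer who follows 15.6.2 literally would print a non-significant p-value for a result the plan elsewhere calls significant and uses to reject the null. Deciding which statement governs after seeing 9 of 34 would be a post hoc choice on the primary endpoint.

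**Working it through.** **Inputs.** Null 0.15 and alternative 0.35 (15.3); stage 1 n = 9, continue at 2 or more; stage 2 n = 25; reject at 9 or more of 34 (15.4, 15.6.5 table).

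**Step 1: reproduce the plan's figures.** With X1 the stage-1 responders and X2 the stage-2 responders,

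P(reject) = Σ over x = 2 to 9 of P(X1 = x) · P(X2 ≥ 9 − x), X1 ~ Bin(9, p), X2 ~ Bin(25, p).

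- p = 0.15: 0.0474 (15.4 gives 0.047).
- p = 0.35: 0.8107 (15.4 gives 0.811).
- Early termination under the null: P(X1 ≤ 1) = 0.2316 + 0.3679 = 0.5995, as in 15.4.
- Expected size under the null: 9 + (1 − 0.5995) × 25 = 19.0, as in 15.4.

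The design figures are correct.

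**Step 2: run the 15.6.2 test as named.** With X ~ Bin(34, 0.15):

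- P(X ≥ 9) = 0.0587, above 0.05.
- P(X ≥ 10) = 0.0240, below 0.05.

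The test's critical count at one-sided 5% is therefore 10, not 9. Right-sided testing is the reading most favourable to the plan; the two-sided exact p at 9/34 is 0.0865. The Clopper-Pearson 95% interval at 9/34 is 12.9% to 44.4%, which also includes 15%.

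**Step 3: account for the gap.** Null probability of reaching 9 or more along the stopped paths:

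- X1 = 0: 0.2316 × P(X2 ≥ 9) = 0.2316 × 0.00797 = 0.0018.
- X1 = 1: 0.3679 × P(X2 ≥ 8) = 0.3679 × 0.02547 = 0.0094.

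The sum is 0.0112, and 0.05866 − 0.04744 = 0.0112. The futility stop explains the whole difference.

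**Step 4: consequence if the 15.6.2 p-value decides.** Two-stage operating characteristics, continuing at 2 or more of 9:

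| Final cutoff | Alpha (ORR 15%) | Power (ORR 35%) |
|---|---|---|
| 9/34 | 0.0474 | 0.8107 |
| 10/34 | 0.0206 | 0.7433 |

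**Step 5: how often it matters.** At 8 or fewer both rules fail; at 10 or more both succeed. They differ only at exactly 9 (after passing stage 1):

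| True ORR | P(exactly 9/34) | Share of all results with ≥ 9/34 |
|---|---|---|
| 15% | 2.7% | 57% |
| 25% | 11.7% | 28% |
| 35% | 6.7% | 8% |

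The maximum is 11.9%, near an ORR of 26.5%.

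**Step 6: totals other than 34.** Assumption: stage 1 stays at 9 with continuation at 2 or more. Critical counts at 5%:

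| n | One-sample count (p) | Two-stage count (alpha; power) |
|---|---|---|
| 33 | 9 (0.0495) | 9 (0.0408; 0.794) |
| 34 | 10 (0.0240) | 9 (0.0474; 0.811) |
| 35 | 10 (0.0292) | 10 (0.0246; 0.767) |

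For n = 30 to 38 the two counts differ only at 34, the planned total; they differ again at 39 (11 versus 10). Keeping 9 as the cutoff at n = 35 would give a two-stage alpha of 0.0546.

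**The case against.** The strongest reply is that the decision rule is already clear. Sections 2.6.1, 15.4 and 15.6.5 all give 9 of 34, no section states 10, and 15.6.5 can be read as supplying the rejection region for the test named in 15.6.2. On that reading alpha and power are exactly as stated, and power of 0.743 is hypothetical. The disagreement covers one outcome, involves no excess false positives, and bears on a claim of preliminary efficacy from a single-arm phase 2 trial. The clause for totals other than 34 might also be called a separate topic.

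Much of this stands. The boundary is the more natural governing rule, the design figures are right, and the reach is narrow. But reading 15.6.5 as the rejection region does not change what the named test prints: 0.0587 at the plan's own success boundary. The plan gives no instruction to adjust that p-value or set it aside. The clause on other totals belongs here because 15.4 says only approximately 34, and a cutoff of 9 carried over to 35 patients would exceed 5%.

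**Conclusion.** The concern holds. The test named in 15.6.2 does not reproduce the rejection region that the plan states elsewhere and on which its alpha and power rest. At 9/34 it gives p = 0.0587, against 0.0474 over the two-stage sample space. Applied as the criterion, it would raise the cutoff to 10 and lower power from 0.811 to 0.743.

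The risk is a disputed conclusion at one outcome, with no inflation of type I error at n = 34. It should be fixed before the analysis, but it does not undermine the design.

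The figures assume exactly 9 and 25 evaluable patients per stage (except where other totals are shown) and continuation at 2 or more of 9. The text of 15.6.5, which stops at 2 or fewer, conflicts with that continuation rule. That is a separate point and must be reconciled first: with continuation at 3 or more, the 9/34 rule would have alpha 0.0294 and power 0.632.

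**What to change.** In 15.6.2, replace the one-sample binomial test with wording to this effect:

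- The primary decision rule is the Simon boundary in 15.4 and the 15.6.5 table.
- The one-sided p-value is computed over the two-stage sample space (0.047 at 9/34). If the trial stops at stage 1, the null is not rejected.
- If the number of efficacy-evaluable patients is not 34, the boundary is the smallest count whose two-stage type I error is at most 5%.

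Keep the observed ORR and the 95% Clopper-Pearson interval, labelled descriptive, so that an interval including 15% at 9/34 is not read as overturning the decision.

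The cost is a few sentences of SAP text and a few lines of code for the two-stage p-value. Sample size, enrolment and data collection do not change.

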15.6.3 Analysis of Secondary Endpoint(s)

PFS and OS will be analyzed using Kaplan-Meier product-limit estimates. Median PFS and OS and the cumulative probability of PFS at 3, 6, and 12 months and cumulative probability of OS at 6, 12, and 18 months will be presented with two-sided 95% confidence interval (CI) if estimable. PFS censoring rules will follow Food and Drug Administration (FDA) Guidance for Industry, Clinical Trial Endpoints for the Approval of Cancer Drugs and Biologics (2007). The KM

estimates of cumulative PFS and OS will be plotted over time with 95% CI if estimable.

15.6.4 Safety Analyses

Safety analyses will be performed using the Safety Analysis set. Safety data include adverse events and lab data will be summarized using descriptive statistics. AE and Severe AE will be summarized by count and percentages by relationship to study drugs, by grade and by patient characteristics. Categorical lab data will be summarized by number and percentage. Continuous lab data will be summarized using n (number of subjects with available data), mean, standard deviation (SD), median, and range (minimum and maximum) unless otherwise specified. General safety will be assessed by the monitoring and recording of all AEs and serious adverse events (SAEs), regular monitoring of hematology and blood chemistry, regular measurement of vital signs, ECG, and the performance of physical examinations (PE) and other safety assessments in line with local regulations governing a study of this nature. Laboratory test results will be summarized using 3 categories, hematology, liver and renal, and other clinical chemistry. Hematology and clinical chemistry parameters that are graded by CTCAE v 4.03 will be summarized by CTCAE grade. Shifts from baseline to the worst CTCAE grade will be tabulated.

Progression of nccRCC and signs and symptoms clearly related to the disease progression should not be captured as an AE. Disease progression is a study endpoint and should be captured in the CRF as per the guidelines for reporting disease progression.

In case of life-threatening bleeding, the investigator should discontinue lenvatinib per Synopsis Table for Grade 4 toxicity and treat the subject based on the institution's standard practice. Clinically significant bleeding will be considered as study-specific events and should always be considered as serious important medical events, which will be entered on the adverse event CRF and reported using the procedures for reporting SAEs, even if the study-specific event does not meet other serious criteria.

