1.0 SCHEDULE OF ACTIVITIES

Screening tests may take place no more than 21 days prior to the first day of study treatment. Window for study visits during treatment is +/- 7 days.

	Screening	C1D1	D1 of each subsequent cycle	Q9 wks	EOT	FU ⁴
Informed consent	X					
H&P, PS	X					
Vital signs	X		X			
CBC	X	X	X		X	
Blood chemistry ⁹	X		X			
Pregnancy test ¹	X ³					
TSH	X		X			
INR	X		X			
Urinalysis	X					
UPCR		X	X			
ECG	X					
CT or MRI ⁸	X			X	X	
Pembrolizumab		X	X			
Lenvatinib ²		X-----X ²				
Research tissue collection ⁷	X					
Research blood collection	X ⁵	X ⁵	X ⁶		X	
Adverse events	X-----X					
Progression and survival						X

1. Women of childbearing potential only
2. Lenvatinib is to be self-administered daily on each day of every 21-day cycle
3. Within 72 hours prior to first dose
4. After coming off treatment, patients will be followed every 12 weeks +/- 1 week until death for survival. If patients discontinue treatment prior to progression, patients will continue to be followed by scans approximately every 9 weeks until progression or the start of another anti-cancer therapy.
5. To be drawn at screening or C1D1 (up to 14 days prior to the start of treatment)
6. C4D1 only
7. Archival from within 3 months (preferred), up to 6 months acceptable; if no biopsy has been performed in the 6 months prior to treatment start then an SOC biopsy should take place after a patient has been determined to be eligible for the trial, if safe and feasible. See section 10.0 for more details.
8. Scans should continue every 9 weeks regardless of cycle length. See Section 12 for further instructions of timelines for obtaining confirmatory scans. For responses, or progression, a confirmatory scan should be performed at least 4 weeks after the initial scan showing progression or response.
9. Albumin, alkaline phosphatase, total bilirubin (and direct bilirubin if total bilirubin is above ULN), bicarbonate, BUN, calcium, chloride, creatinine, glucose, phosphorus, potassium, total protein, AST, ALT, sodium

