15.5 Population for Analyses

- Safety Analysis set: refers to the set of participants who take at least one dose of the study interventions and will be used for safety analysis.
- Efficacy Analysis set: refers to the participants who take at least two cycles of the combined study interventions and have baseline and at least one tumor assessment after receiving treatments unless discontinued due to disease progression, death or toxicity. Subjects received less than 2 cycles of combination treatments will be replaced with additional participants. Efficacy analysis set will be used as the primary set for ORR and other efficacy endpoints.
- Per-Protocol Analysis set: refers to the participants who follows the protocol without major violation and have received at least 80% of the targeted dosage. This set will be used for sensitivity analyses of the efficacy endpoints.

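### No liver or renal panel is scheduled after the last Day 1 visit: the calendar marks CBC but not blood chemistry at end of treatment

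*Combined protocol and SAP*

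**What the plan says.** Section 15.6.4 lists the means of assessing general safety as AE recording, "regular monitoring of hematology and blood chemistry, regular measurement of vital signs, ECG, and the performance of physical examinations (PE" and other assessments. It reports laboratory results in three groups, one of which is liver and renal, and adds: "Shifts from baseline to the worst CTCAE grade will be tabulated".

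The Schedule of Activities (Section 1.0) fixes when the data are collected. Footnote 9 defines the chemistry panel, which begins "Albumin, alkaline phosphatase, total bilirubin (and direct bilirubin if total bilirubin is above ULN), bicarbonate, BUN, calcium, chloride, creatinine" and also holds AST and ALT. The panel is marked at screening and on Day 1 of each cycle after the first. CBC is marked at those visits, at C1D1, and at EOT. The ECG row and the row for history, physical examination and performance status are marked at screening only. No footnote adds to these rows, and Sections 7.1.3 and 7.1.6 refer back to the calendar for liver tests and calcium.

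Four other provisions bear on the point:

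- Baseline: "Screening tests may take place no more than 21 days prior to the first day of study treatment".
- The Safety Analysis set (Section 15.5): "refers to the set of participants who take at least one dose of the study interventions". The same section says: "Subjects received less than 2 cycles of combination treatments will be replaced with additional participants".
- Missing data (Section 15.6.1): "Data will be analyzed as observed and no data imputation will be performed".
- Timing of the last visit (Section 2.6.1): the treatment phase runs "until completion of the off-treatment assessments (within 30 days after the last study drug administration").

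**The concern.** A baseline-to-worst-grade table needs at least one value after baseline, and it shows only what was measured. Blood is drawn at EOT for CBC and for research samples, but the panel with the liver and renal tests is not run there. A patient who stops everything in cycle 1 stays in the safety set with only a screening panel. For other patients, a silent liver or renal change after the last Day 1 draw would not be looked for by any scheduled test.

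The protocol itself gives reasons to look. Section 7.2 warns that pembrolizumab events may appear months after the last dose, and its table bases action on AST/ALT, bilirubin and creatinine. Appendix C, part H, defines a liver event of clinical interest purely by laboratory values (AST or ALT at least 3 times ULN, bilirubin at least 2 times ULN, alkaline phosphatase below 2 times ULN). Section 8.1.3.4 requires such events to be reported through 90 days after treatment, or 30 days if new anticancer therapy starts.

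Separately, Section 15.6.4 names ECG and physical examination as means of assessing safety, while the calendar schedules neither after screening.

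**Working it through.** The plan states no figure on this point, so there is none to reproduce. The check is a comparison of calendar rows and some counting.

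**1. Calendar rows (Section 1.0)**

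| Row | Screening | C1D1 | Day 1, later cycles | EOT |
|---|---|---|---|---|
| CBC | X | X | X | X |
| Blood chemistry | X | – | X | – |
| ECG | X | – | – | – |
| H&P, PS | X | – | – | – |

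The CBC row reaches the EOT column with the nine-week column left blank, so the columns are intact in the text and the empty chemistry cell is real.

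**2. Scheduled panels after the first dose.** Let a patient stop all therapy in cycle *k* and attend no later Day 1 visit. I assume that the C1D1 CBC is drawn before dosing, so it is not counted.

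- Chemistry = Day 1 of cycles 2 to *k* = *k* − 1.
- CBC = (*k* − 1) + 1 at EOT = *k*.
- Stop in cycle 1: chemistry 0, CBC 1. Stop in cycle 2: chemistry 1, CBC 2.

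If EOT falls on a Day 1 visit, chemistry is drawn there anyway and the difference is 0.

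**3. Time from the last scheduled chemistry to EOT.** Let *d* be the cycle day of the last dose (1 to 21) and *e* the days from that dose to EOT (at most 30, Section 2.6.1).

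- No further Day 1 visit: gap = (*d* − 1) + *e*. The maximum is (21 − 1) + 30 = 50 days.
- Stop decided at the next Day 1 visit after a Day 21 dose: that draw is 1 day after the last dose, so gap = *e* − 1, from 0 to 30 − 1 = 29 days.

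The ±7-day visit window is not counted. The 50-day case needs a Day 21 last dose, no following Day 1 draw, and EOT at its limit, all together.

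**4. Who has no scheduled post-baseline chemistry.** Only patients who stop both drugs before C2D1. Section 6.1 counts cycles continuously through dose interruptions, and Section 2.6.1 lets a patient stop one drug and continue the other. C2D1 chemistry stays scheduled in both situations.

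**5. Share of the safety set.** The documents do not say how many patients will stop that early. One patient is 1/34 = 2.9%, or 1/35 = 2.9% if replaced. If, purely as an assumption, 1 to 3 patients did so without replacement, the share would run from 2.9% to 3/34 = 8.8%.

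**6. ECG and examination.** Scheduled after screening: 0 of each. The graded summaries and shifts in Section 15.6.4 cover hematology and chemistry, so this does not touch the shift tables.

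**The case against.** The strongest reply is that there is no conflict over chemistry. Section 15.6.4 promises regular monitoring, and a panel on Day 1 of every cycle from cycle 2 is regular. Nothing there promises an EOT panel. This stands: the missing EOT mark is a gap worth closing, not a broken commitment.

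Second, worst grade is not restricted to scheduled draws. Section 7.1.3 allows liver tests when clinically indicated, the Section 7.2 table suggests weekly or more frequent liver tests after an elevation and calls for renal monitoring, Section 6.8 follows patients removed for unacceptable events until these resolve or stabilize, and Appendix C foresees unscheduled testing. This also stands. It leaves out only change that nobody suspects, which is what a scheduled panel is for.

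Third, the ECG and examination mismatch is mostly wording. The word regular attaches to the laboratory tests and vital signs, and no ECG or examination output is planned. A reader might infer from the QT warning in Section 6.3.2 that the plan commits to on-treatment ECGs and fails to schedule them. The documents do not support that: the warning concerns co-medication, the screening ECG serves the QTc exclusion in Section 4.2, and the general table in Section 7.1 covers lenvatinib toxicity of any kind. What remains is that the analysis text names assessments that the calendar does not collect on treatment.

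**Conclusion.** The gap is real, narrow and cheap to close. No liver or renal panel is scheduled after the last Day 1 visit, and a patient who stops all therapy before C2D1 can enter the chemistry shift tables only through an unscheduled test. The uncovered interval up to EOT is 0 to 50 days, the upper end being an extreme. The affected group is probably small, and its size is not in the documents. The conclusion rests on the calendar as printed and on no other section scheduling the test; I found none.

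Three stronger readings should be resisted:

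- That every patient lacks one chemistry panel. This fails whenever EOT falls on a Day 1 visit.
- That the shift tables cannot be produced, or must end at the last Day 1 draw. Day 1 chemistry supports them for anyone who reaches C2D1, and unscheduled results count.
- That safety reporting or the trial's decisions are compromised. Adverse events are tracked for 120 days after treatment (Section 8.0), and neither the response endpoint nor the stopping rules depend on an EOT panel.

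The ECG and examination mismatch is secondary and editorial.

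**What to change.** 1. Mark blood chemistry at EOT in the Schedule of Activities, run on the draw already taken there for CBC and research blood. The cost is at most one routine panel per patient, and none where EOT coincides with a Day 1 visit. Sample size and the primary analysis do not change. A patient who stops in cycle 1 then has one scheduled post-baseline panel, within 30 days of the last dose.

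2. Align Section 15.6.4 with the calendar by wording alone, for example: *ECG and the protocol-required physical examination are done at screening; on-treatment QTc is not systematically evaluated.* This adds no procedure. On-treatment ECGs are not needed to settle this point.
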